11 PARTICIPANT CONFIDENTIALITY

No participants will be enrolled into this protocol. No samples will be collected as a part of this study. Human participant data obtained during retrospective chart review will not be identifiable directly or through secondary identifying information. Participant confidentiality is held strictly in trust by the participating investigators, their staff, and the sponsor(s) and their agents. The study protocol, documentation, data and all other information generated will be held in strict confidence. No information concerning the study or the data will be released to any third party without prior written approval of the sponsor. Participant information collected in this study will comply with the standards for protection of privacy of individually identifiable health information as promulgated by HIPAA (Health Insurance Portability and Accountability Act) and as mandated in Title 45 CFR Parts 160 and 164. All data records will be kept confidential, and the participant's name will not be released at any time. Participant data records will not be released to anyone other than the Sponsor or its designees and responsible regulatory authorities when requested. In all cases, caution will be exercised to assure the data are treated confidentially and that the participant's privacy is guaranteed.

12 INFORMED CONSENT PROCESS

This study does not involve the enrollment of participants, thus no informed consent is required. The Safety evaluation via a review of medical charts by the PI or their representatives cannot be practically performed if informed consent is required of each participant. Therefore, a waiver of informed consent for the retrospective chart review will be requested from the Institutional Review Board (IRB).

D
T
D

13 SOURCE DOCUMENTS AND ACCESS TO SOURCE DATA/DOCUMENTS

During the chart review process, each participating site will meet regulatory and institutional requirements for the protection of confidentiality of participants. Each site will permit authorized representatives of the sponsor, its designees, and appropriate regulatory agencies to examine (and, when required by applicable law, to copy) clinical records for the purposes of quality assurance reviews, audits, and evaluation of the study safety and progress. These representatives will be permitted access to all source data, which include, but are not limited to, hospital records, clinical and office charts, laboratory notes, memoranda, participants' memory aid or evaluation checklists, pharmacy dispensing records, recorded data from automated instruments, copies or transcriptions certified after verification as being accurate and complete, microfiches, photographic negatives, microfilm or magnetic media, x-rays, and participant files and records kept at the pharmacy, at the laboratories, and medico-technical departments involved in the clinical trial. Data collection forms will be derived from the eCRFs and provided by EMMES, the Data Coordinating Center (DCC), to assist chart review.

14 QUALITY CONTROL AND QUALITY ASSURANCE

The principal investigator will provide direct access to all trial-related sites, source data/documents, data collection forms, and reports for the purpose of monitoring and auditing by the sponsor, and inspection by local and regulatory authorities. The principal investigator will ensure that all study personnel are appropriately trained and applicable documentations are maintained on site. The DCC will implement quality control procedures beginning with the data entry system and generate data quality control checks that will be run on the database. Any missing data or data anomalies will be communicated for prompt clarification and resolution.

D
T
D

15 ETHICS/PROTECTION OF HUMAN PARTICIPANTS

15.1 Ethical Standard

The investigator will ensure that the study will be conducted in accordance with the protocol, the ethical principles of Good Clinical Practice (ICH E6) that have their origin in the Declaration of Helsinki, and all applicable local regulations. The investigator will ensure the study is conducted in accordance with the provisions as stated and will comply with the prevailing local laws and customs.

15.2 Institutional Review Board

The investigator will ensure that the protocol is reviewed and approved by the appropriate Institutional Review Board (IRB) prior to the start of any study activities. The IRB will be appropriately constituted and will perform its functions in accordance with FDA regulations, ICH GCP guidelines, and local requirements as applicable.

15.3 Participant Confidentiality

No participants will be enrolled in this protocol. Data obtained from the PPRU, POPS, and Redac studies will be used for the analyses detailed in this protocol. Data obtained from the PPRU, Redact and POPS studies will be coded; participants will be identified by code numbers and not by name. Data obtained from the Pediatrix database will be de-identified as defined by the HIPAA Privacy Rule (45 CFR 164.514 (a) and (b)).

Appropriate and adequate provisions for ensuring participant privacy and data confidentiality will be maintained by the participating investigators, their staff, the sponsor(s), and their agents. The study protocol, documentation, data, and all other information generated by this study will be maintained in a secure manner and will be kept confidential as required by law. Data access will be limited to study personnel and the data will be stored on servers which have limited physical access (e.g. locked rooms) and limited electronic access (e.g. password controlled access to data, computers and, if applicable, networks). No information concerning the study or the data will be released to any third party without prior written approval of the sponsor.

Study records, including medical and pharmacy records, may be reviewed in order to meet federal or state regulations. Reviewers may include the Food and Drug Administration (FDA), IRBs, the sponsor and its representatives, or the NIH.

15.4 Study Discontinuation

Not applicable. No participants will be enrolled in this study. Prescription of study drug is not part of this protocol.

16 DATA HANDLING AND RECORD KEEPING

The investigator is obligated to conduct this study in accordance with U.S. Federal Regulation 21 CFR 312.60-69 as specified on the signed form FDA 1572, applicable state laws, and the International Conference on Harmonization, Good Clinical Practice, Consolidation Guideline.

During chart review, the investigator(s) at participating site(s) will ensure the accuracy, completeness, legibility, and timeliness of the data reported. Data reported in the eCRF should be consistent with the data collection form/source documents, or the discrepancies should be documented. DCRI and/or EMMES will provide guidance to investigators on making corrections to the data collection forms and eCRFs.

16.1 Data Management Responsibilities

All data collection forms must be reviewed by the clinical team and data entry staff, who will ensure that they are accurate and complete. Data collection is the responsibility of the clinical trial staff at the site under the supervision of the site principal investigator. During the study, the investigator must maintain complete and accurate documentation for the study.

The EMMES Corporation will serve as the DCC for this study and will be responsible for data management, quality review, analysis, and reporting of the study data

16.2 Data Capture Methods

Clinical data (including AEs) obtained through chart review will be entered into a 21 CFR Part 11-compliant internet data entry system provided by the EMMES Corporation. The data system includes password protection and internal quality checks, such as automatic range checks, to identify data that appear inconsistent, incomplete, or inaccurate. Clinical data will be entered directly from the data collection forms/source documents.

16.3 Types of Data

Data for this study will include PK and safety.

16.4 Timing/Reports

Not applicable

16.5 Study Records Retention

Records and documents pertaining to the conduct of this study will be stored for a minimum of 2 years following the last approval of a marketing application in an ICH region and until there are no pending or contemplated marketing applications in an ICH region, or at least 2 years have elapsed since the formal discontinuation of clinical development of the investigational product.

16.6 Protocol Deviations

Not applicable

16.7 Participant Privacy/Authorization

The principal investigator will ensure that the use and disclosure of protected health information obtained during a research study complies with the HIPAA Privacy Rule. The rule provides U.S. federal protection for the privacy of protected health information by implementing standards to protect and guard against the misuse of individually identifiable health information of participants of clinical trials.

17 PUBLICATION POLICY

Following completion of the study, the investigator may publish the results of this research in a scientific journal under the oversight of the Publication Committee of the Pediatric Trials Network. The PTN Publication Committee comprises representatives of the network cores, thought-leaders, DCC, and PTN and is responsible for generation and coordination of the publications that report scientific findings of the network. All public presentations (abstracts, manuscripts, slides and text of oral or other presentations, and text of any transmission through any electronic media) by participating investigators, participating institutions, DCC, and PTN that use PTN data and are intended to represent the PTN or are supported by the PTN will be reviewed by the Publication Committee per the Publication Committee charter.

The Publication Committee guarantees that the study results are presented by experts in the field that have working knowledge of the study design, implementation, data synthesis/analysis, and interpretation. The committee goals are to ensure that any confidential or proprietary information is protected, and that all appropriate statistical analyses have been included.

The PTN Publication Committee will adhere to the trials registration policy adopted by the International Committee of Medical Journal Editors (ICMJE) member journal. This policy requires that all clinical trials be registered in a public trials registry such as ClinicalTrials.gov, which is sponsored by the National Library of Medicine. Other biomedical journals are considering adopting similar policies. It is the responsibility of the IND holder to register this trial in an acceptable registry. Any clinical trial starting enrollment after 01 July 2005 must be registered on or before patient enrollment. For trials that began enrollment prior to this date, the ICMJE member journals will require registration by 13 September 2005, before considering the results of the trial for publication.

The ICMJE defines a clinical trial as any research project that prospectively assigns human participants to intervention or comparison groups to study the cause-and-effect relationship between a medical intervention and a health outcome. Studies designed for other purposes, such as to study pharmacokinetics or major toxicity (e.g., phase I trials), would be exempt from this policy.

All investigators funded by the NIH must submit or have submitted for them to the National Library of Medicine's PubMed Central an electronic version of their final, peer-reviewed manuscripts upon acceptance for publication, to be made publicly available no later than 12 months after the official date of publication. The NIH Public Access Policy ensures the public has access to the published results of NIH-funded research. It requires investigators to submit final peer-reviewed journal manuscripts that arise from NIH funds to the digital archive PubMed Central upon acceptance for publication. Further, the policy stipulates that these papers must be accessible to the public on PubMed Central no later than 12 months after publication.

Refer to:

<http://publicaccess.nih.gov/>

<http://grants.nih.gov/grants/guide/notice-files/NOT-OD-08-033.html>

19 APPENDIX

Table 4. Diagnoses

Body System	Diagnoses	Serious Diagnoses
Gastrointestinal	Medical NEC	Surgical NEC
		Focal intestinal perforation
Neurologic	Grade II IVH	Grade III or IV IVH
	Periventricular leukomalacia	Cystic periventricular leukomalacia
		Seizure
Cardiovascular	PDA requiring medical treatment	PDA requiring surgical treatment
	Hypotension requiring pressors	Cardiorespiratory arrest
	Tachycardia	
Ophthalmology		ROP requiring laser surgery
Hematology		Hyperbilirubinemia requiring exchange transfusion
Dermatology	Rash	
Respiratory	Tachypnea	

IVH=intraventricular hemorrhage
 PDA=patent ductus arteriosus

NEC=necrotizing enterocolitis
 ROP=retinopathy of prematurity

Table 5. Laboratory Values

Laboratory Values	Abnormality	Serious Abnormality
Serum Electrolytes		
Hypoglycemia	< 40 mg/dL	< 20 mg/dL
Hyperglycemia	> 250 mg/dL	> 400 mg/dL
Hyponatremia	< 125 mmol/L	< 115 mmol/L
Hypernatremia	> 150 mmol/L	> 160 mmol/L
Hyperkalemia	> 6 mmol/L	> 7.5 mmol/L
Hypokalemia	< 3 mmol/L	< 2.5 mmol/L
Hypercalcemia (iCa)	> 12.5 mg/dL (>1.5 mmol/L)	> 13.5 mg/dL (>1.6 mmol/L)
Hypocalcemia (iCa)	< 6.0 mg/dL (<0.9 mmol/L)	< 5.0 mg/dL (< 0.8 mmol/L)
Hypermagnesemia	> 3.5 mg/dL	> 4.5 mg/dL
Hypomagnesemia	< 1.5 mg/dL	< 1.2 mg/dL
Hyperphosphatemia	> 9.5 mg/dL	> 10.5 mg/dL
Hypophosphatemia	< 3.5 mg/dL	< 2.5 mg/dL
Base Excess	< -10 mmol/L	< -15 mmol/L
Renal Dysfunction		
Elevated BUN	> 70 mg/dL	> 100 mg/dL
Elevated Creatinine	> 1.7 mg/dL	> 3.0 mg/dL
Liver Dysfunction		
Elevated AST	> 5 x upper limit of normal	> 10 x upper limit of normal
Elevated ALT	> 5 x upper limit of normal	> 10 x upper limit of normal
Elevated GGT	> 5 x upper limit of normal	> 10 x upper limit of normal
Direct bilirubin	> 5 mg/dL	>10 mg/dL
Complete Blood Count		
Leukocytosis	> 25,000/mm ³	> 40,000/mm ³
Leukopenia	< 5000/mm ³	< 2000/mm ³
Neutropenia	< 500/mm ³	< 100/mm ³
Thrombocytopenia	< 100/mm ³	< 30/mm ³
Thrombocytosis	> 600,000/mm ³	> 1,000,000/mm ³

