6.1.2.2 Pediatrix Administrative Database Review

Data will be extracted from the Pediatrix Medical Group Database. The following clinical and demographic variables will be included in addition to date of birth, gestation age, race, ethnicity, sex, and birth weight (Table 3).

Table 3: Variables Collected for Pediatrix Safety Study

	Date of birth	-3 days	-2 days	-1 day	On ampicillin	+1 day	+2 days	+3 days
Adverse Events (new onset)								
Cardiorespiratory arrest					X			
Hypotension					X			
Tachypnea					X			
Tachycardia					X			
Medical NEC					X			
Surgical NEC					X			
Focal intestinal perforation					X			
Grade II IVH					X			
Grade III or IV IVH					X			
Periventricular leukomalacia					X			
Cystic periventricular leukomalacia					X			
PDA requiring medical treatment					X			
PDA requiring surgical treatment					X			
Rash					X			
Seizure					X			
ROP requiring laser surgery					X			
Hyperbilirubinemia requiring exchange transfusion					X			
Laboratory Values								
AST		X	X	X	X	X	X	X
ALT		X	X	X	X	X	X	X
GGT		X	X	X	X	X	X	X
Direct bilirubin		X	X	X	X	X	X	X
WBC count		X	X	X	X	X	X	X
Neutrophil count		X	X	X	X	X	X	X
Hematocrit		X	X	X	X	X	X	X
Platelets		X	X	X	X	X	X	X
BUN		X	X	X	X	X	X	X
Creatinine		X	X	X	X	X	X	X
Glucose		X	X	X	X	X	X	X
Sodium		X	X	X	X	X	X	X
Potassium		X	X	X	X	X	X	X
Calcium		X	X	X	X	X	X	X
Magnesium		X	X	X	X	X	X	X
Phosphorus		X	X	X	X	X	X	X
Base excess		X	X	X	X	X	X	X
Positive Blood/Urine/CSF Cultures								
Organism		X	X	X	X	X	X	X
Ampicillin Dosing								
Days of administration					X			
Clinical Variables								
Mechanical ventilation					X			
Fraction of inspired oxygen					X			
Concomitant medications					X			

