10.4.2 Objective #2

Severity of diagnoses and laboratory values will be assigned according to predetermined definitions (see Appendix tables 4 and 5). A diagnosis (Appendix table 4) will be attributed to ampicillin if it was first made on a day that the infant was exposed to ampicillin. A laboratory abnormality (Appendix table 5) will be attributed to ampicillin if it occurred on a day that the infant was exposed to ampicillin or one day after exposure to ampicillin. For the cohort of patients from the PPRU Antimicrobial PK in High Risk Infants study enrolled at Reda, the frequency of diagnoses and laboratory abnormalities attributed to ampicillin will be described using standard summary statistics. For the patients exposed to ampicillin in the Pediatrix database, the frequency of diagnoses and laboratory abnormalities attributed to ampicillin will be compared to those not attributed to ampicillin. Multivariable logistic regression analyses will be performed to evaluate the association between diagnoses and laboratory abnormalities and ampicillin controlling for clinical factors associated with poor outcome in infants such as mechanical ventilation, inotropic support, and demographic features including race, gender, gestational and postnatal age. Outlier diagnostics and evaluation for multicollinearity will be performed using standard techniques. The full model containing all clinically relevant variables listed above will be compared to scaled down models using likelihood ratio tests, and the most parsimonious model that fits the data will be used for analysis. The odds of a diagnosis or laboratory abnormality occurring on a day the infant was exposed to ampicillin will be compared to the odds of occurrence on a day the infant was not exposed to ampicillin. Odds ratios and 95% confidence intervals derived from this model will be reported.

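### Table 5 sets the thrombocytopenia cut-offs about 1,000-fold too low for the unit printed, so the abnormality would essentially never be counted

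*Protocol*

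**What the plan says.** Table 5 in Section 19 (Appendix) lists the laboratory abnormalities for Objective #2, with one cut-off for an abnormality and one for a serious abnormality. Two adjacent rows concern platelets:

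- "Thrombocytopenia < 100/mm ³ < 30/mm ³"
- "Thrombocytosis > 600,000/mm ³ > 1,000,000/mm ³"

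The leukocyte rows of the same block use the same unit: "Leukocytosis > 25,000/mm ³ > 40,000/mm ³" and "Leukopenia < 5000/mm ³ < 2000/mm ³".

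Section 10.4.2 makes the table operative: "Severity of diagnoses and laboratory values will be assigned according to predetermined definitions", with a pointer to Appendix Tables 4 and 5. The resulting abnormalities are summarised for the chart-review cohort. In the Pediatrix cohort they enter the frequency comparison and the logistic regression: "The odds of a diagnosis or laboratory abnormality occurring on a day the infant was exposed to ampicillin will be compared" with the odds on an unexposed day.

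Platelets are collected in both cohorts (Tables 2 and 3 in Section 6.1.2), from three days before ampicillin to three days after. Neither table gives a unit for the count, and nowhere else does the protocol state a platelet cut-off.

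**The concern.** The two platelet rows describe the low and high ends of one measurement in one printed unit, yet they are not on the same scale. The low row appears to have lost its thousands.

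These cut-offs decide which infant-days count as events. If the low row is applied as printed, a count of 30,000 to 99,999/mm³ (abnormal on the evident intent) and a count below 30,000/mm³ (serious) would both be graded as normal. Thrombocytopenia would then show a frequency of about zero on exposed and unexposed days alike. Because both sides of the comparison fail together, no contrast between them would expose the error. Safety is one of the protocol's two objectives, and Section 2.1.2 gives the poor description of ampicillin safety in neonates as a reason for the study.

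**Working it through.** The protocol gives no sample-size or power figure to reproduce here. The check is one of unit consistency within Table 5.

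**Step 1. Ratio of high to low cut-off.** For each analyte with a cut-off at both ends, ratio = high cut-off ÷ low cut-off. All inputs are from Table 5.

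| Analyte | Abnormality | Serious abnormality |
|---|---|---|
| Platelets, as printed | 600,000 / 100 = 6,000 | 1,000,000 / 30 = 33,333 |
| Leukocytes | 25,000 / 5,000 = 5 | 40,000 / 2,000 = 20 |
| Glucose | 250 / 40 = 6.25 | 400 / 20 = 20 |
| Phosphorus | 9.5 / 3.5 = 2.7 | 10.5 / 2.5 = 4.2 |
| Magnesium | 3.5 / 1.5 = 2.3 | 4.5 / 1.2 = 3.75 |
| Calcium (mg/dL) | 12.5 / 6.0 = 2.1 | 13.5 / 5.0 = 2.7 |
| Potassium | 6 / 3 = 2 | 7.5 / 2.5 = 3 |
| Sodium | 150 / 125 = 1.2 | 160 / 115 = 1.4 |
| Platelets, low cut-offs × 1,000 | 600,000 / 100,000 = 6 | 1,000,000 / 30,000 = 33 |

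Apart from platelets, the ratios run from 1.2 to 6.25 (abnormality) and from 1.4 to 20 (serious). The printed platelet ratios are about three orders of magnitude outside those ranges. After multiplication by 1,000 the abnormality ratio lies inside its range, and the serious ratio is of the same order as the leukocyte and glucose values.

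**Step 2. Does any storage unit make both rows work?**

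- Counts held per mm³, as printed: the thrombocytosis row works; the thrombocytopenia row is essentially never met.
- Counts held in thousands per mm³: the thrombocytopenia row works (100 means 100,000/mm³). Thrombocytosis would then require a stored value above 600,000, that is 600,000 × 1,000 = 600,000,000/mm³, which is never met.

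Either way one row is unusable. If the chart review and the Pediatrix database hold platelets in different units, a different row fails in each cohort.

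**Step 3. Illustration of the size.** The protocol gives no platelet distribution, so this step rests on assumptions: lognormal counts, median 150,000 to 300,000/mm³, standard deviation on the log scale 0.4 to 0.8, and one count for each of the 400,000 exposed infants in Section 10.1.2. Share below cut-off c = Φ[(ln c − ln median) / SD].

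- c = 100: the most favourable case (median 150,000, SD 0.8) gives z = ln(100/150,000) / 0.8 = −9.1. The share is numerically 0, so no events are expected. The same holds for c = 30.
- c = 100,000: from z = ln(100,000/300,000) / 0.4 = −2.75 (0.3%) to z = ln(100,000/150,000) / 0.8 = −0.51 (31%). That is about 1,200 to 122,000 infants.
- c = 30,000: from under 0.0001% to 2.2%, or about 0 to 8,850 infants.

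The width of these ranges shows that the number of missed events cannot be derived from the protocol. The zero under the printed cut-offs holds throughout.

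**The case against.** The inconsistency between the rows is hard to dispute, so the case on the other side concerns its reach.

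- **The unit is not stated at collection.** Loss of nearly all events follows only if counts are held per mm³ and the row is applied literally. This stands as a qualification. It does not rescue the table, because in thousands the thrombocytosis row fails instead, and /mm³ is the unit the table prints.
- **Someone would notice.** A zero in a dataset this large would be conspicuous, and Sections 14 and 16.2 provide for data queries and automatic range checks. But those checks screen data values, not a wrong grading constant, and the range checks in Section 16.2 cover chart-review entries only. A silent correction in programming would also be an undocumented departure from definitions the protocol calls predetermined.
- **The reach is limited.** The odds ratio applies only to Pediatrix; the 60-infant chart review has descriptive statistics only. The 400,000 figure is an upper bound for exposed infants, because only those with a recorded count contribute. Section 2.1.2 raises inhibition of coagulation but does not name platelet counts. All of this stands.
- **It is a slip in one of 24 rows.** The other rows, the diagnoses and the pharmacokinetic objective are untouched, and the analysis could be re-run. This also stands, but the slip sits in an event definition that the analysis uses, not in background text.
- **Digits may have been lost when the PDF was read.** This is unlikely: both thrombocytopenia cells are affected alike, while the row below keeps its thousands in both cells.

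**Conclusion.** The point holds. As printed, the thrombocytopenia row is wrong by a factor of about 1,000 relative to its neighbour, and the table cannot grade both low and high platelets from one variable. With counts per mm³, essentially all true thrombocytopenia, abnormal and serious, would be graded normal in both cohorts. In Pediatrix the odds ratio would have no events on either side and could not be estimated.

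The contradiction between the rows needs no assumption beyond the table itself. Two things are inferred: the exact factor of 1,000, which is strongly supported by the other rows but stated nowhere, and the choice of failing row, which depends on the storage unit. The damage is confined to one abnormality in Objective #2 (thrombocytopenia, or thrombocytosis if counts are in thousands), but that outcome is unusable as defined and must be corrected before the definitions are programmed.

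**What to change.** 1. The sponsor confirms the intended thrombocytopenia cut-offs and corrects the row to the scale of the thrombocytosis row. On the evident intent these are below 100,000/mm³ (abnormality) and below 30,000/mm³ (serious abnormality). Expressing both platelet rows in thousands per mm³ would serve equally well.
2. State the platelet unit once and convert counts from the chart review and the Pediatrix database to it before grading.
3. Add a platelet range check after conversion, in both cohorts, so that values left in the wrong unit are caught.

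The cost is one table row, one programming constant and a unit check. No new data are needed, and no other definition changes.
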